### **9.1.1 Primary endpoint**

The primary endpoint is:

- Mean/median annualized number of reported total bleeds in patients with hemophilia A,

### **9.1.2 Secondary endpoints**

The secondary endpoints are:

- Occurrence, duration, treatment, severity, and outcome of AEs of special interest (hypersensitivity reactions, loss of drug effect, renal impairment, neurocognitive disorders, and inhibitor development), AEs, SAEs, and ARs.
- Hemostasis during surgery measured by number of infusions and consumption of FVIII product
- Change in joint scores (HJHS) from baseline to 12 months, to 24 months, to 36 months.
- Joint status evaluation by ultrasound (HEAD-US score), if available or part of standard clinical practice.
- Number of affected joints by patient, and the change from baseline to 12 months, to 24 months and to 36 months.
- Annualized number of spontaneous, joint, and trauma bleeds.
- Number of reported bleeds (total, spontaneous, joint, and trauma) during the study compared with number of reported bleeds (total, spontaneous, joint, and trauma) for previous FVIII products in the 12 months prior to enrollment into the study.
- Proportion of patients with 0 bleeds, and the difference in proportion comparing to previous prophylaxis treatment.
- Description of PK parameters for previous FVIII products versus damoctocog alfa pegol (if available in routine clinical practice).
- Efficacy of treatment of break-through bleeds.
- Change from baseline to 12 months, to 24 months and to 36 months in treatment satisfaction (Hemo-SAT A score).
- Change from baseline to 12 months, to 24 months and to 36 months in treatment satisfaction (Hemo-QoL [A and SF] score).

- Change from baseline to 12 months, to 24 months and to 36 months in work productivity and activity impairment (WPAI score).

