## 9. Research methods

### 9.1 Study design

This is a multinational, open-label, prospective, non-interventional, multicenter, cohort study of PTPs with hemophilia A receiving damoctocog alfa pegol with any kind of treatment modality (on-demand, prophylaxis, or intermittent prophylaxis). The study is planned to be conducted in multiple countries depending on timing of regulatory approval and national reimbursement access.

Prospective data will include prophylaxis regimen effectiveness measured by the number of ABR (reported in patient infusion diaries or documented by physicians, if patient infusion diary is not available), drug usage (IU/kg/infusion, IU/kg/year, and IU/kg/event), regimens used, patient-reported outcome (PRO) measurements (where applicable), such as validated, disease-specific and generic quality of life questionnaires and treatment satisfaction; as well as PK parameters (when available), joint outcomes (HJHS), and safety including AEs of special interest (hypersensitivity reactions, loss of drug effect, renal impairment, neurocognitive disorders, and inhibitor development) and drug-related ARs in standard clinical practice. Retrospective data will include documentation of previous therapy, lifetime duration on prophylaxis, medical condition, PK parameters (when available), and bleeds up to 12 months prior to use of damoctocog alfa pegol, in order to allow a stratification of patients by patient bleeding profile and disease characteristics (See Section 9.3.7).

Patients/legal representatives and physicians can choose from different prophylaxis regimens with damoctocog alfa pegol following approved local labels or any other regimen prescribed by the physician as part of normal clinical practice. Patients/legal representatives and physicians can choose to change the dosing regimen based on the patient's response to treatment at any time. A reason for the dose and/or frequency change should be documented.

The patients planned observation period will be 36 months (with the potential for further extension), for the collection of long-term safety data and continuous prospective monitoring of joint health status over time.

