#### **ABR:**

Summary statistics of the number, type, location, and severity of reported bleeds (total, spontaneous, joint, and trauma) will be presented.

The primary analysis on ABR will be performed in patients receiving prophylactic treatment. ABRs will first be characterized using descriptive statistics by calculating mean ( $\pm$  standard deviation [SD]), median, minimum, and maximum. Further, the mean ABRs along with 95% CIs will be estimated using a negative binomial regression model corrected for over-dispersion, and with relevant treatment and disease characteristics as covariates and observed prophylactic treatment period as an offset variable.

When enough data is collected, additional analyses include: 1) comparing the ABR in patients receiving prophylactic treatment with those who are not treated with standard prophylaxis; 2) comparing the ABR in patients receiving damoctocog alfa pegol prophylactic treatment with the ABR prior to the damoctocog alfa pegol treatment.

Further details of the analysis will be described in the SAP.

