**Patients with 0 bleeding events:**

The proportions of bleed-free patients and 95% CIs for the proportions will be presented.

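### Protocol 9.1.2 sets a raw on-study bleed count against a 12-month count, at odds with the ABR comparison in 9.7.4, and gives the zero-bleed difference no common window

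*Protocol*

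**What the plan says.** Protocol 9.1.2 lists a count endpoint, "Number of reported bleeds (total, spontaneous, joint, and trauma) during the study compared with number of reported bleeds", the second count being "for previous FVIII products in the 12 months prior to enrollment into the study". The bullet immediately before it reads "Annualized number of spontaneous, joint, and trauma bleeds", so the list does annualize when it means to. A further bullet is "Proportion of patients with 0 bleeds, and the difference in proportion comparing to previous prophylaxis treatment", with no time window on either side. The matching analysis text in 9.7.4 says only "The proportions of bleed-free patients and 95% CIs for the proportions will be presented".

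On follow-up, 9.1 states "The patients planned observation period will be 36 months", extendable, with up to three further months of documentation. Section 9.7.1 keeps patients with less than three years in the full analysis set. Earlier bleeds are collected for up to 12 months before the start of therapy (9.3.2, 9.3.4).

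The ABR part of 9.7.4 plans, as an additional analysis once data suffice, to compare the ABR on prophylaxis "with the ABR prior to the damoctocog alfa pegol treatment". The Abstract defines ABR as events divided by years on the regimen.

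**The concern.** A count grows with observation time, and the chance of remaining bleed-free shrinks with it. Comparing either one over unequal periods turns a difference in length into an apparent difference in bleeding. The count endpoint is worded in exactly that way, and its wording disagrees with the analysis section. For the zero-bleed difference the periods are left open, but only one side can extend beyond 12 months. Annualizing cannot repair a zero-bleed proportion afterwards; the window has to be fixed.

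The reference period is also inconsistent. Section 9.1.2 counts back from enrollment, while 9.3.2 and 9.3.4 count back from the start of therapy. Patients already on the product at enrollment are eligible. For them the 12 months before enrollment can include time on the study product. If that time is removed because the endpoint refers to previous products, less than 12 months remains. Section 9.7.2 uses first administration for these patients, but only for the baseline summary.

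At stake is how the study describes bleeding before and after the switch: a product with no effect on the rate could appear to raise the bleed count and lower the bleed-free proportion.

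**Working it through.** **Inputs.** From 9.5: negative binomial model, ABR 4 in the earlier trial, planning ABR (mu) 6, dispersion (theta) 1. From 9.1: 36 months on study. From 9.1.2, 9.3.2 and 9.3.4: a 12-month look-back. The range theta 0.5 to 2 is my assumption.

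**The plan's own figure.** With variance mu + mu²/theta, the 95% half width at n = 180 is 1.96 × sqrt((6 + 36)/180) = 0.947; on the log scale it is 0.951. Table 4 states 0.96. The log-scale values for n = 36 and 108 are 2.16 and 1.23, against 2.17 and 1.23 stated. The model is therefore read as intended. At theta = 1 the alternative form mu + theta × mu² is identical; at other values it only swaps the 0.5 and 2 rows below.

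**Counts at an unchanged rate.** The expected count is mu × T, with T in years.
- ABR 4: 12 months gives 4, 36 months gives 12. Ratio 3.0.
- ABR 6: 6 against 18. Ratio 3.0.
- With 24 months of follow-up the ratio is 2.0. In general it equals the mean follow-up in years.

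**Zero bleeds at an unchanged rate.** If each patient has a constant rate and rates vary between patients as a gamma distribution, P(0 bleeds in T years) = (theta/(theta + mu × T))^theta. For theta = 1 and mu = 4 this is 1/5 at 12 months and 1/13 at 36 months.

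| ABR | theta | 12 months | 24 months | 36 months | 36 minus 12 (points) |
|---|---|---|---|---|---|
| 4 | 1 | 20.0% | 11.1% | 7.7% | -12.3 |
| 6 | 1 | 14.3% | 7.7% | 5.3% | -9.0 |
| 4 | 0.5 | 33.3% | 24.3% | 20.0% | -13.3 |
| 4 | 2 | 11.1% | 4.0% | 2.0% | -9.1 |
| 6 | 0.5 | 27.7% | 20.0% | 16.4% | -11.3 |
| 6 | 2 | 6.3% | 2.0% | 1.0% | -5.3 |

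If the years were independent within a patient, the fall would be steeper: 20.0% to 0.8% (0.2³) at ABR 4, theta 1.

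**Short follow-up.** Below 12 months the sign reverses. Taking 6 months purely as an illustration, ABR 4 and theta 1 give 1/(1 + 2) = 33.3% against 20.0% over 12 months.

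**On equal footing.** With rates per year, or zero bleeds over 12 months on both sides, the same unchanged rate gives a rate ratio of 1.0 and a zero-bleed difference of 0.

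**The case against.** The best defence is that 9.7.4 already plans the before/after bleed comparison on the ABR scale, and nothing in 9.7 plans a raw 36-month against 12-month contrast. This stands to a large extent: a reader might infer from 9.1.2 that raw counts will be compared, but the protocol as a whole does not settle on that. What remains is a conflict. The 9.7.4 comparison is additional and conditional, does not amend the endpoint, and is silent on zero bleeds.

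Second, no 36-month or 12-month window is written for the zero-bleed endpoint. That is correct. The mismatch is inferred from the collection periods, and the SAP, not available here, may set a window. The endpoint is nevertheless a difference between two periods, one of which cannot exceed 12 months, so the protocol should name the common length.

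Third, a reader might infer that early interim publications will flatter the product. The documents do not support that. The Abstract describes the first interim as one of baseline characteristics. Section 9.1 is broader, but no section schedules a zero-bleed contrast at an early interim, and the 6-month figure is not the protocol's.

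Fourth, prior modality is not ignored. Section 9.7.1 provides for stratification and regression with pre-treatment history as a covariate, and the zero-bleed endpoint is tied to previous prophylaxis. The before/after ABR text itself, however, does not separate patients who were previously treated on demand.

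**Conclusion.** The count endpoint in 9.1.2 is mis-worded and conflicts with 9.7.4. Read literally, it shows a threefold rise at 36 months with no change in rate, and proportionately less for shorter follow-up. The zero-bleed difference needs a common window. Over the full study, an unchanged rate gives a spurious fall of 12.3 points at ABR 4 and 9.0 points at ABR 6 with theta 1, and 5.3 to 13.3 points over the assumed dispersion range. These figures assume 36 months for every patient, a 12-month look-back, and a constant rate within each patient. Drop-out makes the real artefact smaller, and it reverses for patients followed for under 12 months.

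It would go too far to call these endpoints the only comparisons with previous therapy: 9.7.4 compares ABRs, and 9.1.2 and 9.7.8 compare pharmacokinetics. They are secondary endpoints in a study without hypothesis testing, and the primary endpoint is annualized. This is a should-fix.

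**What to change.** 1. In 9.1.2, restate the count endpoint as annualized rates on both sides, paired within patient, using a negative binomial model with log time as offset, consistent with 9.7.4.
2. In 9.1.2 and 9.7.4, define the zero-bleed proportion over equal 12-month windows, on study and before treatment. State a rule for patients with under 12 documented months on either side. For example, any observed bleed counts as not bleed-free; those without an observed bleed are shown both ways, as bleed-free and as not; and a sensitivity analysis covers early switchers. Do not simply drop them: observation ends at a permanent switch (9.2.7), so a completers-only analysis could remove patients who bled and then switched, which would inflate the on-study proportion.
3. Use one reference period throughout, and say how it applies to patients already on the product at enrollment.
4. Show the before/after ABR comparison by prior modality.

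The cost is wording, a little more analysis, and less information from patients with short follow-up. Bleed dates (9.3.7) and prior modality (9.3.4) are already collected, so no new data are needed.

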## 9.2 Setting

### 9.2.1 Eligibility

All PTPs with hemophilia A receiving damoctocog alfa pegol with any kind of treatment modality (on-demand, prophylaxis, or intermittent prophylaxis), will be eligible to be enrolled into the study. Indications and contra-indications according to the local market authorization should be carefully considered.

### 9.2.2 Eligibility criteria

#### 9.2.2.1 Inclusion criteria

- Diagnosis of hemophilia A.
- Patients previously treated for Hemophilia A.
- Patients without previous history of inhibitors or patients with previous history of inhibitors on standard prophylaxis therapy for at least 1 year prior to study entry.
- No current evidence\* of FVIII inhibitor or clinical suspicion\*\* of FVIII inhibitor.
  - \* Evidence of FVIII inhibitor as measured by the Nijmegen-modified Bethesda assay [ $<0.6$  Bethesda units (BU/mL)] or Bethesda assay [ $<1.0$  BU/mL] in 2 on consecutive samples.
  - \*\* Documented or clinical suspicion of shortened FVIII half-life ( $<6$  hours).
- Initiation of or currently on damoctocog alfa pegol with any kind of treatment modality (on-demand, prophylaxis, or intermittent prophylaxis).
- Signed informed consent/assent.

#### 9.2.2.2 Exclusion criteria

- Concurrent participation in an investigational program with interventions outside of routine clinical practice.
- Diagnosis of any other bleeding/coagulation disorder other than hemophilia A.
- Contra-indications according to the local marketing authorization.
- Patient on immune tolerance induction (ITI) treatment at the time of enrollment.

### 9.2.3 Rationale for specific exclusion criteria

Patients with diagnosis of any other bleeding/coagulation disorder other than hemophilia A, contra-indications according to the local marketing authorization (including patients who have history of hypersensitivity reactions to the active substance, mouse or hamster protein, or other constituents of the product and patients with active FVIII inhibitors), and patients on ITI treatment will not be included according to the labeled indication and contra-indications, as a positive benefit-risk has not been established for these patient populations.

#### **9.2.4 Withdrawal**

In this observational study, withdrawal from the study is independent of the underlying therapy and will not affect the patient's medical care. Each patient may withdraw from the study at any time and without giving a reason. If a patient/legal representative (in case of minors) wants to terminate study participation, no further data will be collected. In case a patient/legal representative would like to withdraw the consent given earlier, s/he should inform his/her doctor and the site should document the withdrawal in the electronic Case Report Form (eCRF) as well as in the patient medical records.

#### **9.2.5 Replacement**

Patients will not be replaced after dropout.

#### **9.2.6 Representativeness**

The eligibility criteria have been selected to allow for a broad representation of patients within the study. The study will enroll previously treated hemophilia A patients initiating or currently receiving damoctocog alfa pegol with any kind of treatment modality (on-demand, prophylaxis, or intermittent prophylaxis). Prophylaxis therapy is the recommended standard of care for patients with severe disease and those with moderate disease with severe patient bleeding profile. By enrolling eligible patients with mild, moderate, or severe disease, the study will be representative of real-world.

Previously untreated hemophilia A patients are not eligible for this study as the safety of damoctocog alfa pegol in this patient population has not been established. Given the incidence rate of hemophilia A, 1 in 5,000 live male inhabitants, previously untreated patients represent approximately 2% of the hemophilia patient population. Thus, the study population is broadly representative of mild, moderate, and severe hemophilia A patients, even when previously untreated patients are excluded.

In addition, the inclusion of a representative sample of study sites (i.e., health care providers, hospitals, etc.) in terms of geography, practice size, and academic or private practice type is aimed as a measure to enhance the generalizability of study results.

The patients documented in the study should be selected based only on eligibility according to a minimal set of selection criteria (see Sections 9.2.2 and 9.2.3). No further selection should be applied, thus increasing the generalizability of the study results. Physicians will be asked to sample consecutive patients whenever possible. This consecutive sampling approach is intended to reduce selection bias by the treating physicians as to whom to enroll in the study, especially with regard to factors that may be associated to the outcome or prognosis of those patients (e.g., demographic characteristics, multiple co-morbidities, as well as concomitant medications), thus maintaining the observational character and enhancing the external validity of the study. Furthermore, an anonymous patient log file (integrated in the Electronic Data Capture [EDC] system) will be used by each site to document also patients not enrolled in the study (without recording patient-specific data), including the reason for not enrolling (e.g., refused consent, eligibility criteria not met, etc.).

The sample of study sites should, ideally, reflect the distribution of hemophilia A treatment settings in each participating country in the background of the specific local health system. Nevertheless,

the final sample of study sites will strongly depend on the willingness of physicians to participate in the study.

### **9.2.7 Visits**

The physician documents a first visit that corresponds to the initiation of the observational period (initial visit/baseline) in the eCRF/EDC system. Follow-up visits occur during routine practice, the study protocol does not define exact referral dates for those visits. After the initial visit, data collection will continue for 36 months (with the potential to be extended). Data collection occurs continuously throughout the observational period, i.e. each visit or assessment is to be documented in the eCRF/EDC system. Typical information to be collected are summarized in [Table 3](#).

#### **Enrollment/Initial visit**

Once a patient is found to be eligible for inclusion, the physician will inform the patient and legal representative (where applicable) about the study. This will include discussing the informed consent/assent form and asking the patient/legal representative to read and - upon agreeing to participate - sign the informed consent/assent form (see Section 10.4).

Baseline information is recorded with the status at the initial visit before the first drug administration after enrollment into the study.

#### **Follow-up data collection period**

The follow-up assessments will be completed in the eCRF/EDC system. These assessments do not require the scheduling of any additional visits outside of the standard of care.

Due to the observational nature of the study no specific follow-up visits can be scheduled and it is unknown when a patient will come for the next visit. Thus data collection occurs continuously throughout the 3 year observational period, i.e. each visit or assessment is to be documented in the eCRF/EDC system. Final data collection should be no sooner than 36 months after the initial visit. For that reason the data documentation period will continue up to 3 months post Month 36 for the final follow-up timepoint.

Allocation of a visit or assessment to a specific follow-up timepoint (e.g. Month 12, 24 and 36 after initial visit) will be done during statistical analysis and will further be described in the Statistical Analysis Plan (SAP).

In case a patient is seen by more than 1 physician (e.g., the patient is monitored by a physician other than the initial treating physician), the initial treating physician should make every effort to collect information on any visits (including results) that have taken place outside the treating physician's site for example by communicating with the other physician or by having the patient/legal representative obtain a letter with detailed information and results, for example of any ARs, medications given, or procedures performed.

#### **End of observation and final safety follow-up**

The final data collection (end of observation) should be no sooner than 36 months after initiation of the observational period, except where the study initiator decides to extend the study, or where documentation is no longer possible, such as where the patient/legal representative withdraws consent, is lost to follow-up, death, switch to other therapy (permanently stop damoctocog alfa pegol), or the decision to terminate the study.

A final safety follow-up (collection of AEs) will be up to 30 days after receiving the last therapy within the study period.

**Lost to follow-up**

A patient is regarded as ‘Lost to follow-up’ in case no further information can be expected from the patient at a given point in time.

In case no information was obtained from a patient within 24 month since the last data collection time point the site personnel is requested to apply due diligence – within the applicable legal limits – to contact patients to ascertain the reason. In case no information can be retrieved, the site should confirm that the patient is lost to follow-up and document the end of observation.

**Table 3: Tabulated overview on data collected during the study**

	Enrollment/ Initial visit	Follow up visit (including end of observation)
Eligibility Assessment (see 9.2.2)	X	
Date	X	X
Demographic data (see 9.3.3)	X	
General medical/surgical history (see 9.3.5)	X	
Disease history (see 9.3.4)	X	
Bleed history (see 9.3.1)	X	
Prior FVIII treatment history (see 9.3.4)	X	
Damoctocog alfa pegol history (if any, see 9.3.7)	X	
Current prescribed damoctocog alfa pegol regimen (see 9.3.7)	X	X
Damoctocog alfa pegol dose/regimen changes, treatment switches (see 9.3.7)		X (Continuous collection)
Patient-Reported Data (Hemo-SAT A, Hemo-QoL-A, Hemo-QoL Short Form, WPAI [+ CIQ: HS]; see 9.3.10)	X	X (Month 12, 24, 36)

	Enrollment/ Initial visit	Follow up visit (including end of observation)
Physical examination (weight, height, vital signs) 	X	X
Joint Health (HJHS)	X	X
Ultrasound data 	X	X
Affected joints	X	X
Damoctocog alfa pegol Pharmacokinetic analysis  (see 9.3.7)	X	X
Concomitant medication (see 9.3.6)	X	X
Adverse events (includes systematically collected AEs and AEs of special interest (see 11)) 	X (Continuous collection)	
Inhibitor 	X	X
Patient infusion diary		X (Continuous collection)
Physician recorded bleeds 		X (Continuous collection)
Physician recorded surgeries		X (Continuous collection)
Reason for end of observation (see 9.3.11)		X (once, at occurrence)

 Routine examinations only, if available.

 PK analysis is at physician's discretion. PK testing (and the frequency of testing per the table) is part of the routine use of the product.

 Adverse events (up to 30 days after the last treatment with damoctocog alfa pegol in study period).

 Serious, life-threatening bleeds and surgery bleeds to be recorded by the physician. Physician to ask patient at each visit regarding bleeds.

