### **Hemophilia Treatment Satisfaction Questionnaire (Hemo-SAT)**

This is a hemophilia-specific treatment satisfaction questionnaire. The Hemo-SAT questionnaire version for adults (Hemo-SAT A) consists of 34 items pertaining to 6 dimensions (Ease & Convenience, Efficacy, Burden, Specialist/Nurses, Center/Hospital, General Satisfaction). The Hemo-SAT A questionnaire is suitable for adult patients and adolescents (>12 years of age) and should be completed at the initial (baseline) visit, at Month 12, Month 24 and Month 36.

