### **Hemophilia Quality of Life Measure for Adults (Hemo-QoL-A) and Hemo-QoL Short Form (Hemo-QoL-SF) for Children and Adolescents**

The questionnaire is used to capture the full impact of damoctocog alfa pegol and the treatment modalities on the patients' hemophilia-specific quality of life. Hemo-QoL-A is a hemophilia-specific quality of life questionnaire for adults aged 18 years and above. The questionnaire has 41 items covering 6 domains: Physical Functioning, Role Functioning, Worry, Consequences of Bleeding, Emotional Impact, and Treatment Concerns. For patients younger than 18 years, the Hemo-QoL-SF Questionnaire for children and adolescents (12 to 17 years) is used. The Hemo-QoL-SF contains 35 questions covering 9 domains: Physical Health, View of Yourself, Family, Friends, Others, Sports, Dealing, and Treatment. The respondent burden for both questionnaires is approximately 15 minutes. Patients should complete the Hemo-QoL (A or SF) questionnaire at the initial (baseline) visit, at Month 12, Month 24 and Month 36.

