## **Work Productivity and Activity Impairment Scale (WPAI)**

The study will include the Work Productivity and Activity Impairment: Hemophilia Specific (HS) questionnaire also containing classroom impairment questions (CIQ) (WPAI [+ CIQ: HS]).

The WPAI questionnaire has been widely used in PRO work since its initial development over 20 years ago. There have been approximately 40 validation studies regarding the use of this tool in various chronic disease states, as well as for general health. In addition to the validation studies, there are documented uses of the tool in various chronic conditions including hemophilia. A hemophilia specific questionnaire is also available and translated in many languages. It has been recently used in several studies [29].

The WPAI [+ CIQ: HS] assesses the effect of hemophilia on ability to work, attend classes, and perform regular daily activities in ages 12 and above. The questionnaire is self-administered and comprises nine questions that elicit information on work, classroom, and daily activity impairment during the previous seven days. Scores are expressed as percentages of impairment/ productivity loss, with higher scores indicating greater impairment. The respondent burden for this questionnaire is approximately 10 minutes. The assessment should be performed at the initial (baseline) visit, at Month 12, Month 24 and Month 36.

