### **9.7.6 Analysis of patient-reported outcomes**

Analysis of PRO will be performed on the FAS, and if needed and data permits, subgroup analysis may be performed based on the subgroups defined in Section 9.7.1.

Appropriate scores for questionnaires will be derived and changes from baseline will be analyzed by summary statistics. Patients with improved, unchanged, and worsened scores will be presented using a shift table. Further details of the analysis will be described in the SAP.

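### No patient-reported outcome is requested when observation ends before Month 36, so the score at a switch away from the drug is not collected and each later change score rests on patients still observed

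*Protocol*

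**What the plan says.** **Schedule.** The follow-up column of Table 3 is headed "Follow up visit (including end of observation". The PRO row is the only one in that column tied to nominal months: "X (Month 12, 24, 36". HJHS and affected joints carry an unqualified X there. The only row triggered by the end of observation is the reason for it: "X (once, at occurrence".

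Section 9.4 repeats the PRO schedule for each instrument:
- Hemo-SAT A: "should be completed at the initial (baseline) visit, at Month 12, Month 24 and Month 36"
- Hemo-QoL: "Patients should complete the Hemo-QoL (A or SF) questionnaire at the initial (baseline) visit, at Month 12, Month 24 and Month 36"
- WPAI: "The assessment should be performed at the initial (baseline) visit, at Month 12, Month 24 and Month 36"

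**End of observation.** Section 9.2.7 lists the events that end observation before Month 36. Besides withdrawal of consent, loss to follow-up and death, the list includes "switch to other therapy (permanently stop damoctocog alfa pegol), or the decision to terminate the study".

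**Analysis.** Section 9.1.2 defines the PRO endpoints as changes from baseline to Months 12, 24 and 36. Section 9.7.6 analyses them on the full analysis set (FAS) and adds: "Patients with improved, unchanged, and worsened scores will be presented using a shift table". Section 9.7.1 says that outcomes are in general not imputed. It leaves likelihood and imputation methods open where imputation is needed, with details to follow in the SAP.

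**The concern.** A patient who changes product at, say, Month 8 has baseline questionnaires and nothing afterwards. One who changes at Month 20 has nothing after Month 12. In both cases the patient's view of the treatment when giving it up is not requested.

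The loss may well be informative. Section 7.3 links poor adherence to the time burden and inconvenience of prophylaxis, and Hemo-SAT A has dimensions for convenience, efficacy and burden. The instrument measures what could plausibly make a patient leave. If leavers have the worse scores, mean change and the shift table look better at each successive landmark partly because the less satisfied patients are no longer there. PROs are a secondary objective, and Section 7.2 says the results may be used to educate patients, payors and providers.

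This belongs in the protocol and not only in the SAP. The SAP can set visit windows and choose a missing-data method, but it cannot add a questionnaire that was never scheduled.

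**Working it through.** **1. Is an exit PRO requested anywhere?** Table 3, the three questionnaire descriptions in Section 9.4, the endpoints in 9.1.2 and the end-of-observation text in 9.2.7 agree with one another, and none asks for one. The HJHS row makes a useful comparison. Its endpoint in 9.1.2 uses the same three landmarks, yet its Table 3 entry is not restricted to them, so a joint score at an early end of observation falls within the schedule and a PRO does not.

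**2. The plan's own figure.** Section 9.5 takes 200 patients and 10% dropout: 200 × (1 − 0.10) = 180. This reproduces, and it implies 20 leavers. It is a dropout figure for the effectiveness analysis. The protocol gives no switch rate and no PRO standard deviation.

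**3. When the leavers go.** Assume a constant exit rate with total share d over 36 months. Leavers by month t = 200 × [1 − (1 − d)^(t/36)].

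| d | Month 12 | Month 24 | Month 36 |
|---|---|---|---|
| 5% | 3.4 | 6.7 | 10 |
| 10% (protocol) | 6.9 | 13.6 | 20 |
| 20% | 14.3 | 27.6 | 40 |
| 30% | 22.4 | 42.3 | 60 |

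At 10%, about 7 of 200 leave before Month 12 and would normally have no post-baseline PRO. The other 13 or so (20 − 6.9 = 13.1) remain under observation to Month 12 at least and can contribute a change score there.

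**4. Possible shift in the mean change at Month 36.** Let S be the mean change in stayers. Let L be the mean change in leavers at their last on-treatment point. The mean over everyone is (1 − d) × S + d × L, so the stayers' mean differs from it by d × (S − L). With S − L assumed, in SD units:

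| d | 0.25 SD | 0.5 SD | 1.0 SD |
|---|---|---|---|
| 10% | 0.025 | 0.05 | 0.10 |
| 20% | 0.05 | 0.10 | 0.20 |
| 30% | 0.075 | 0.15 | 0.30 |

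**5. What an exit PRO could add.** At most 20 extra scores per 200 patients at 10% exit, and 60 at 30%. The real number is smaller, because some exits are withdrawals of consent, losses to follow-up or deaths.

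**6. Denominator.** The local amendment for Japan (Annex 6) removes the PROs for 60 Japanese patients. The protocol does not say whether these 60 are among the 200. If they are, the PRO base is 200 − 60 = 140, and the number leaving before Month 12 at 10% exit is 140 × 6.9/200 = 4.8.

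**The case against.** The strongest reply is that the schedule and the endpoints match, so the document contains no contradiction. The PROs are secondary and descriptive, with no hypothesis test. Section 9.7.1 tabulates reasons for discontinuation by time point, and Section 9.9 names selection bias and PRO bias as limitations. All of this is true. It discloses the problem without reducing it.

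A reader might infer several stronger things, which the protocol does not support:

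- *That the change scores describe only persisters.* This holds for each landmark taken alone. Patients who leave after Month 12 or 24 count at the earlier landmarks, and the FAS keeps patients without three full years of follow-up (Section 9.7.1).
- *That nothing can be done at analysis.* Likelihood methods and multiple imputation remain open, and earlier scores, bleeds and the reason for leaving could inform them, under assumptions. The allocation of assessments to time points is also left to the SAP, so a score given near a nominal month may still count. What these methods cannot supply is the observed score at the switch. For a patient who leaves before Month 12, carrying the last value forward would carry the baseline and record no change.
- *That most other rows in Table 3 are secured at exit.* Physical examination and inhibitor results are collected only where routine practice provides them. Of the comparison rows, HJHS and affected joints carry no such limit.
- *That an exit visit always occurs.* Follow-up visits are not scheduled, and questionnaires are completed at routine visits (Sections 9.2.7 and 9.3.10). An exit PRO can only be conditional on such a visit.
- *That a corrected share of worsened patients at Month 36 can be calculated.* The 10% is not a switch rate, the worsening share among leavers is unknown, and an exit score is not a Month 36 value.

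**Conclusion.** The gap is real but limited. The plan requests no PRO at an early end of observation, so the score at a permanent switch is not collected and each landmark result rests on the patients still observed.

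The number leaving before the first follow-up questionnaire is about 7 of 200, given the protocol's 10% dropout and an assumed constant exit rate. A lean towards improvement is plausible if dissatisfaction or burden drives switching, but it is not established, since patients may switch for other reasons. Its size is unknown. With an assumed difference of 0.5 SD between leavers and stayers, it is 0.05 SD at 10% exit, which is small, and 0.15 SD at 30%. It grows with attrition over the 36 months. This is a cheap improvement, not an error in the plan.

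**What to change.** 1. In Table 3 and in each questionnaire description in Section 9.4, change the PRO timing to: *baseline, Month 12, 24, 36, and at end of observation if earlier, where a routine visit takes place*. Limit this to the countries where the PROs apply.
2. In Section 9.7.6, add change from baseline to the last on-treatment assessment, with its shift table, as a supplement to the Month 12, 24 and 36 results. Show it separately for patients who stopped the drug and those who stayed. The SAP can define which assessments count as on treatment.

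**Cost.** About 25 minutes of questionnaires (15 for Hemo-QoL plus 10 for WPAI, per Section 9.4) plus Hemo-SAT A, for early leavers only. No new instrument or extra visit is needed and treatment is not affected, so the non-interventional design is kept.

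**Limit.** There will be no exit score after withdrawal of consent, loss to follow-up or death, or where no routine visit takes place. The change reduces the informative loss but does not remove it.
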